1.2. Study Objectives

1.2.1. Long-Term Extension Period Objectives (Part B)

The objectives of the Long-Term Extension (LTE) Period of this study are to assess the following in subjects with ALS:

- Disease progression, survival, neuropsychological function, respiratory function, motor/limb and bulbar function, and effects on biomarker activity upon long-term treatment with PTC857
- Safety and tolerability upon long-term treatment with PTC857
- Quality of life upon long-term treatment with PTC857
- PK of PTC857

1.2.2. Continued Long-Term Extension Period Objectives (Part C)

- The objectives of the Continued LTE Period of the study are to assess the following in subjects with ALS:
- Safety and tolerability upon continued long-term treatment with PTC857
- Disease progression and survival upon continued long-term treatment with PTC857
- Quality of life upon continued long-term treatment with PTC857

1.3. Study Endpoints

1.3.1. Long-Term Extension Period Endpoints (Part B)

The LTE Period endpoints of this study are the following:

- Severity and number of TEAEs and TESAEs, change in clinical laboratory tests, physical examination, vital signs, and 12-lead ECGs during the LTE Period
- Change from baseline in ALSFRS-R after 52 weeks of treatment
- Change from baseline in slow vital capacity as assessed by PFTs after 52 weeks of treatment
- Change from baseline in motor/limb and bulbar function as assessed by the Modified Norris Scale after 52 weeks of treatment
- Change from baseline in neuropsychological function as assessed by the ALS CBS after 52 weeks of treatment
- Survival after 52 weeks of treatment
- Quality of life as assessed by ALSAQ-40 after 52 weeks of treatment
- Quality of life as assessed by EQ-5D-5L after 52 weeks of treatment
- Change from baseline in blood and urine biomarker activity after 52 weeks of treatment
- PK of PTC857

1.3.2. Continued Long-Term Extension Period Endpoints (Part C)

The Continued LTE Period endpoints of this study are the following:

• Severity and number of TEAEs and TESAEs during the Continued LTE Period

- Change from baseline in ALSFRS-R after 160 weeks of treatment
- Survival after 160 weeks of treatment
- Quality of life as assessed by ALSAQ-40 after 160 weeks of treatment

1.4. Randomization and Blinding

Subjects who satisfy all the inclusion and none of the exclusion criteria will be randomly assigned in a 2:1 ratio to receive one of the following two treatment arms during the 24-week treatment phase according to a study randomization scheme:

- Arm 1: PTC857 (250 mg) administered orally BID for 24 weeks.
- Arm 2: Matching placebo administered orally BID for 24 weeks.

Investigators, subjects and site staff will be blinded to treatment assignments during the entire study period. PTC biostatistics staff who are directly involved in the analysis of the study results and members of the clinical study team will remain blinded to the treatment assignment throughout the conduct of Part A and will be unblinded after the first database lock for Part A.

Participation in the long-term extension periods does not involve randomization.

2. ANALYSIS SETS

2.1. All Enrolled Set

The All-Enrolled set will contain all subjects who signed an informed consent for this study. This analysis set will be used to summarize subject disposition.

2.2. Intent-to-Treat (ITT) Analysis Sets

Intent-to-Treat 1 Analysis Set (ITT1)

All subjects who are randomized after the Screening Period and take at least 1 dose of double-blind study drug in the Treatment Period and who have a decrease in the ALSFRS-R score of ≤4 points during the Screening Period will be included in the ITT1 Analysis Set. Subjects will be analyzed according to their randomized treatment.

Intent-to-Treat 2 Analysis Set (ITT2)

All subjects who are randomized after the Screening Period and take at least 1 dose of double-blind study drug in the Treatment Period will be included in the ITT2 Analysis Set. Subjects will be analyzed according to their randomized treatment assignment. ITT2 analysis set will be used as supportive analysis population.

2.3. Safety Analysis Set

All subjects in the ITT2 Analysis Set who receive at least 1 dose of study drug will be included in the Safety Analysis Set. Subjects will be analyzed according to the actual treatment received.

2.4. Long-Term Extension Safety Analysis Set

All subjects who receive at least one dose of the open-label study drug during the long-term extension periods will be included in the LTE Safety Analysis Set.

2.5. Per Protocol Set

All subjects in the ITT1 Analysis Set who have no major protocol deviations that affect the validity of the efficacy measurements will be included in the PP Analysis Set. The PP Analysis Set will be used for sensitivity analysis of the efficacy endpoint.

2.6. Pharmacokinetic Analysis Set

All subjects in the ITT2 Analysis Set who have at least 1 measurable post-baseline plasma or CSF PTC857 concentration will be included in the PK Analysis Set. Subjects with protocol violations that could affect the PK parameters will be assessed by the pharmacokineticist for inclusion into the PK analysis set. The pharmacokineticist may also exclude subjects or specific concentrations from the PK parameter calculation if required, for example if doses were missed or if samples were collected out of the allowed assessment windows. PK summaries and analyses will be conducted using the PK analysis set. The PK analysis set will be based on the actual treatment received.

2.7. Protocol Deviations

A protocol deviation is defined as any intentional or unintentional change to, or noncompliance with, the approved protocol procedures or requirements. Deviations may result from the action or inaction of the subject, investigator, or site staff. Examples of deviations include, but are not limited to, the following:

- Failure to adhere to study exclusion and inclusion criteria
- Failure to comply with dispensing or dosing requirements
- Use of medications that are specifically prohibited in the protocol
- Missed or out-of-window visits
- Drug dosing not administered within the time frame specified in the protocol
- Failure to adhere to test requirements, including vital signs, laboratory tests, physical examinations, PK blood draws, medical history, etc (either the tests were not done, the incorrect tests were done, or the tests were not done within the time frame specified in the protocol)
- Procedural deviations such as incorrect storage of study drug, failure to update the ICF when new risks become known, or failure to obtain IRB/IEC approvals for the protocol and ICF revisions

Major protocol deviations are defined in the study's Protocol Deviation Handling Plan and include quality issues that have a high likelihood to significantly impact a subject's rights, safety or well-being, or have a potentially significant impact on data integrity.

Protocol deviations will be documented separately in a stand-alone file before database lock which include deviation category (e.g., violation of inclusion and exclusion criteria at screening, use of excluded concomitant medications, received the wrong treatment or incorrect dose), deviation description, severity (minor/major), visit/time point for each deviation.

3. GENERAL CONSIDERATIONS

3.1. General Considerations

Continuous data will be summarized using number of observations (n), arithmetic mean (mean), standard deviation (SD), median, minimum value (min) and maximum value (max). Additionally, for biomarker data, the summaries will include geometric means and geometric standard deviations, as appropriate. Categorical variables will be summarized using the frequency count (n) and percentage (%).

For all percentage calculations, the denominator will be the number of subjects in the analysis set, unless otherwise stated.

Only data from protocol scheduled visits will be included in the summary tables. Data from unscheduled visits will not be included in the summary tables but will be included in the bysubject listings. Descriptive summaries by visit will be provided for all the primary and secondary efficacy endpoints.

3.2. Data Definitions and Analysis Issues

3.2.1. Study/Onset Day

The study/onset day will be defined as the number of days after the first dose of study drug, which is assigned as Day 1 for analysis purposes. Study/onset day is calculated using the formula below:

Assessment Date Relative to First Dose of Study Drug	Study Day Calculation
Assessment/Event date prior to date of first dose	Date of assessment – Date of first dose of study drug
Assessment/Event date on or after Date of first dose	(Date of assessment – Date of first dose of study drug) +1

3.2.2. Weeks Since Initial Dose of Investigational Product (PTC857)

Nominal visits for subjects initiating open-label PTC857 in Part B will be aligned with those who initiated PTC857 during the double-blind period (Part A).

This alignment allows for the evaluation of changes from initial exposure for scheduled assessments (e.g., laboratory tests, and vital signs) for subjects initiating PTC857 at different periods of the study, i.e., those randomized to active drug in Part A at the randomization visit (Day 1) and those randomized to placebo and initiating active drug in Part B. The display below illustrates the matching of these two groups.

Study Day LTE period	Study Day Double-blind period	Weeks since initial exposure to PTC857
Day 169	Day 1	0
Day 183	Day 14	2
Day 197	Day 29	4
Day 225	Day 57	8
Day 253	Day 85	12

Day 365	Day 113	28
Day 393	Day 141	32
Day 449	NA	40
Day 533	NA	52
Day 617	NA	64
Day 701	NA	76
Day 785	NA	88
Day 869	NA	100
Day 953	NA	112
Day 1037	NA	124
Day 1121	NA	136
Day 1149	NA	140

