| ALSAQ-40 | | | | | Х | X | | Х |
| EQ-5D-5L | | | | | Х | Х | | Х |
| C-SSRS ^r | | | X | Х | Х | Х | X | Х |
| Study drug dispensation | X | | | | Х | | | |
| Adverse events | | Χ | X | X | X | X | X | X |
| Prior/concomitant medications | | Χ | X | X | X | X | X | X |
| Mammogram ^s | X | | | | | X | | X ^t |

Abbreviations: ALS, amyotrophic lateral sclerosis; ALS CBS, ALS Cognitive Behavioral Screen; ALSAQ-40, ALS Assessment Questionnaire; ALSFRS-R, ALS Functional Rating Scale-Revised; BMI, body mass index; CAFS, Combined Assessment of Function and Survival; CSF, cerebrospinal fluid; C-SSRS, Columbia-Suicide Severity Rating Scale; ECG, electrocardiogram; EOS, end of study; EQ-5D-5L, five-level European quality of life five-dimensional questionnaire; ET early termination; ICF, Informed Consent Form; IH, in-home; IP, In-person; LTE, Long-Term Extension; PC, telephone call; PFT, pulmonary function test; PI, Principal Investigator; PK, pharmacokinetic

^a Follow-up Visit on Day 393 only for subjects who choose not to enter the Continued LTE Period (Part C).

^b For subjects who early terminate from the study and consent to continued follow-up, the investigator should attempt to gain vital status on the participant and conduct the ALSFRS-R assessment approximately every 28 days for the remaining duration of the study, in accordance with local requirements/regulations.

Day 365 will be considered the End of Treatment Visit only for those who choose not to enter the Continued LTE Period (Part C).

^d For the telephone call/in-home visit, where applicable, the ALSFRS-R, C-SSRS, adverse events, and prior/concomitant medications assessments will be conducted via a telephone call. Vital signs assessments and samples for clinical laboratory tests will be collected via a home health nurse during applicable inhome visits at the subject's home during these visits. Subjects may go to the site for an in-person visit at the discretion of the PI. Visits indicated as in-person only may be conducted remotely (ie, in-home) following discussion between the site and the medical monitor. In-person visits that are conducted remotely must include the following assessments, at minimum (if such assessments are typically included during the visit): serum/urine pregnancy test (females only), vital signs, clinical laboratory tests, ALSFRS-R, C-SSRS, adverse events, prior/concomitant medications, sparse PK blood sampling, laboratory biomarkers, and ALSAQ-40.

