6.4. Vital Signs

Vital signs including systolic and diastolic blood pressure (mmHg), pulse rate (beats/min), body temperature (°C), Oxygen saturation (SpO₂), and respiratory rate (breaths/min) will be evaluated

at Screening, Day 1, Day 29, Day 57, Day 85, Day 113, Day 141, and Day 169, as well as the ET visit where applicable.

For convenience, the conversion for temperature: Temperature (in $^{\circ}$ C) = (Temperature [in $^{\circ}$ F]-32) x (5/9).

Absolute results and changes from baseline will be summarized descriptively by visit for each parameter, by treatment group and overall.

6.5. 12-Lead Electrocardiogram

The following 12-lead ECG will be performed at Screening, Day 1, Day 85, and Day 169, as well as the ET visit where applicable.

- Heart rate (bpm)
- QRS Interval (msec)
- PR Interval (msec)
- QT interval (msec)
- QTcF Interval (msec)
- Overall Interpretation

Descriptive summaries will be presented for the ECG parameter values and change from baseline by visit for all quantitative measurements. Overall interpretation of ECG assessment will be summarized by counts and percentages. QT and QTcF will be categorized as follows, and the category based on actual value will be summarized by treatment group at each visit as well as the category at each post-baseline visit based on change from baseline per the following criteria:

Type of Value	Category 1	Category 2	Category 3
Actual value	> 450 ms	> 480 ms	>500 ms
Change from Baseline	> 30 ms	>60 ms	

A by-subject listing of all ECG parameters will be provided.

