6.5. Vital Signs

Vital signs including systolic and diastolic blood pressure (mmHg), pulse rate (beats/min), body temperature (°C), Oxygen saturation (SpO2), and respiratory rate (breaths/min) will be evaluated at Screening, Day 1, Day29, Day57, Day 85, Day 113, Day 141, Day 169, Day 197, Day 225, Day 253, Day 365, Day 533, Day 701, Day 869, and Day 1037 as well as the ET visit where applicable.

For convenience, the conversion for temperature: Temperature (in $^{\circ}$ C) = (Temperature [in $^{\circ}$ F]-32) x (5/9).

Absolute results and changes from baseline will be summarized descriptively by visit for each parameter, by treatment group and overall.

6.6. 12-Lead Electrocardiogram

The following 12-lead ECG will be performed at Screening, Day 1, Day 85, Day 169, Day 253, Day 365, Day 533, Day 701, Day 869, and Day 1037 as well as the ET visit where applicable.

- Heart rate (bpm)
- QRS Interval (msec)
- PR Interval (msec)
- QT interval (msec)
- QTcF Interval (msec)
- Overall Interpretation

Descriptive summaries will be presented for the ECG parameter values and change from baseline by visit for all quantitative measurements. Overall interpretation of ECG assessment will be summarized by counts and percentages. QT and QTcF will be categorized as follows, and the category based on actual value will be summarized by treatment group at each visit as well as the category at each post-baseline visit based on change from baseline per the following criteria:

Type of Value	Category 1	Category 2	Category 3
Actual value	> 450 ms	> 480 ms	>500 ms
Change from Baseline	> 30 ms	>60 ms	

A by-subject listing of all ECG parameters will be provided.

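### In the Parts B/C SAP, the exposure-week table puts Part A Days 113 and 141 (weeks 16 and 20) in the week-28 and week-32 rows; separately, the LTE adverse-event window stops at Part C entry although Parts B and C are pooled

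*SAP*

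**What the plan says.** **Alignment table (Parts B/C SAP, section 3.2.2).** The rule is that "Nominal visits for subjects initiating open-label PTC857 in Part B will be aligned with those who initiated PTC857 during the double-blind period (Part A". The purpose is stated: "This alignment allows for the evaluation of changes from initial exposure for scheduled assessments (e.g., laboratory tests, and vital signs". The table has three columns: LTE study day, double-blind study day, and weeks since first exposure to PTC857. Two of its rows read "Day 365 Day 113 28" and "Day 393 Day 141 32". From week 40 on, the double-blind column is marked not applicable.

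**Day count (section 3.2.1).** For dates on or after the first dose, study day is "Date of assessment – Date of first dose of study drug) +1".

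**Schedules.** The Part A SAP, section 6.4, takes vital signs "at Screening, Day 1, Day 29, Day 57, Day 85, Day 113, Day 141, and Day 169". The Parts B/C SAP, section 6.5, repeats the Part A days ("Day 113, Day 141, Day 169, Day 197, Day 225") and goes on to Days 253 and 365, but does not list Day 393. Protocol Table 2 has neither vital signs nor laboratory tests on Day 393, and its footnote a reads "Follow-up Visit on Day 393 only for subjects who choose not to enter the Continued LTE Period (Part C".

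**Adverse-event window (Parts B/C SAP, section 6.3.1).** Events count as LTE events from the first open-label day until 30 days after the last open-label dose, or until just before the Continued LTE begins if that is earlier. Section 3.4 combines Part B and Part C safety data, section 6.1.1 reports them pooled, and section 6.3.1 itself promises TEAE summaries for both parts. Section 3.2.6 carries the open-label period to the last dose in Part B or C plus one day.

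**The concern.** The table exists so that subjects who started PTC857 on Day 1 (early start) and those who started at Day 169 (late start) can be compared at equal exposure. A row that pairs different exposure times defeats that purpose, and a programmer who follows the table would build the error into the output. The display most plausibly affected is the summary over Parts A, B and C, which section 6.1.1 puts in a single column. The B+C tables keep the two start groups apart.

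The adverse-event rule is a different kind of problem. Its closing parenthesis mirrors the one in the Part A SAP, section 6.2. There, the window hands over to an LTE window that is defined. Here, it hands over to a Part C window that section 6.3.1 does not define. Under section 3.3, available safety data from Parts B and C are summarized in the interim study report at the Part A lock, so both rules will be needed early.

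**Working it through.** **Inputs.** Day count from section 3.2.1; table rows from section 3.2.2; visit schedules from Protocol Tables 1 and 2.

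**Formulas.** Early start: weeks = (day − 1)/7. Late start: weeks = (day − 169)/7.

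**The plan's own labels.** The LTE column reproduces the week label in all 17 rows of the table. The seven rows with a double-blind day are:

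| LTE day | Weeks, late start | Double-blind day | Weeks, early start | Label |
|---|---|---|---|---|
| 169 | 0 | 1 | 0 | 0 |
| 183 | 2 | 14 | 1.86 | 2 |
| 197 | 4 | 29 | 4 | 4 |
| 225 | 8 | 57 | 8 | 8 |
| 253 | 12 | 85 | 12 | 12 |
| 365 | 28 | 113 | **16** | 28 |
| 393 | 32 | 141 | **20** | 32 |

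Five of seven agree (Day 14 rounds to week 2). Two do not: 28 − 16 = 12 and 32 − 20 = 12. The week labels fit the LTE days, so the double-blind cells are the ones in error.

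**What would match.** Late-start weeks 16 and 20 are Days 169 + 7×16 = 281 and 169 + 7×20 = 309. Only pregnancy tests are scheduled there, so Days 113 and 141 have no LTE counterpart. Early-start week 28 is Day 1 + 7×28 = 197.

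**Which data are touched.**
- Vital signs, first wrong row: taken on Day 113 and on Day 365, so week 16 would be combined with week 28.
- Vital signs, second wrong row: taken on Day 141 but not on Day 393, so the row would hold only early-start week-20 values under the label 32.
- Laboratory tests: none on Day 113 or Day 141 (Protocol Table 1), so nothing is mixed.

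**Adverse-event window.** No arithmetic is needed to see the conflict. For a subject who enters Part C, section 6.3.1 ends the window the day before Part C starts, while sections 3.4 and 6.1.1 and the TEAE-table text in 6.3.1 need it to cover Part C. Section 3.2.6 does reach into Part C, but it defines a treatment period, not an adverse-event rule, and it stops one day after the last dose rather than 30.

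**The case against.** The strongest reply is that neither slip is tied to a specified output. Section 3.2.2 says its display illustrates the matching, sections 6.4 and 6.5 summarize by visit, and section 3.2.3.1 sets baseline at study Day 1. The adverse-event parenthesis sits beside several passages that plainly intend B+C pooling. This stands in part: the mixing is what following the table would produce, not something a named table is certain to show. But the section does state a purpose, and the cells defeat it.

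Four stronger readings are tempting and are not supported:

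- **That no Part A contact can fall at week 28.** Protocol Table 1 has a Day 197 follow-up call for subjects who do not enter Part B, and section 3.6 counts it as their final Part A visit. It is off treatment, so it does not justify the Day 113 cell, but it exists.
- **That lipid data are corrupted.** Lipoprotein change is the one potential risk listed in Protocol section 1.5.3, and the early-start Day 197 visit in Part B does include laboratory tests. That visit is merely unmatched: its data are still collected and summarized by visit. Leaving open-label early-start days unmatched is also consistent with the table's later rows.
- **That 79% of open-label safety data are lost.** Part C is (1121 − 365)/7 = 108 of (1121 − 169)/7 = 136 open-label weeks, and 108/136 = 79%. This is a ceiling on time, for a subject who completes Part C, under a literal reading. It does not count events. The TEAE definition has no end date, and all events are listed.
- **That exposure-adjusted rates are understated.** This would require events to be cut at Part C entry while follow-up runs on. Section 6.3.2 ties follow-up to the reporting period, so it does not follow.

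**Conclusion.** Both points hold as errors in analysis rules, with limited reach. Two of seven paired rows are misplaced by 12 weeks each. For laboratory tests and vital signs, the consequence is confined to vital signs: one row mixed, one row mislabelled. This assumes that the table is programmed as written and that summaries combine the two start groups.

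The adverse-event window in section 6.3.1 conflicts with the pooled reporting in sections 3.4 and 6.1.1 and in 6.3.1 itself, and with the open-label period in section 3.2.6. Taken literally, it leaves Part C events outside the LTE reporting window, but not outside the TEAE definition or the listings. Only subjects who enter Part C are concerned.

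All affected outputs are descriptive. The Part A primary result is untouched. The points should be corrected because they are wrong as written and almost free to fix.

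**What to change.** **Section 3.2.2.** Remove Days 113 and 141 from the week-28 and week-32 rows. Either enter not applicable, or list them separately as weeks 16 and 20 with no LTE match. Optionally, pair late-start Day 365 with the early-start Part B visit on Day 197 at week 28. In that case, rename the double-blind column, because that visit is open-label, and state that the Part A follow-up call on the same day is not used.

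**Section 6.3.1.** For the pooled B+C tables, delete the parenthesis that ends the window at the Continued LTE, so that it runs to 30 days after the last open-label dose in Part B or C. Reconcile this with section 3.2.6.

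**Cost.** Two table cells and one sentence, with a cross-check of section 3.2.6; one more pairing and a column heading if the option is taken. No new data are needed.

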3.2.3. Study Baseline Definition and Change from Baseline

3.2.3.1. Baseline Definition and Change from Baseline

The Baseline Visit will be defined as Day 1 of the study. Unless otherwise stated, for each subject, baseline value of a parameter is defined as the last non-missing measurement taken at most one week prior to the first dose of study drug (including unscheduled assessments). If the last non-missing measurement and the date of first dose of study drug coincide, that measurement will be considered baseline, but AEs and medications commencing on the date of first dose of study drug will be considered post-baseline.

For the purposes of calculating summary statistics of the outcome measures, change from baseline will be derived as follows:

• Change from baseline = Post-baseline value – Baseline value

